#### 6.2 DATA ANALYSIS GENERAL CONSIDERATIONS

#### **6.2.1** Definitions and Computations

Study day: Study day will be calculated in reference to the date of the first dose of study drug. For assessments conducted on or after the date of the first dose of study drug, study day will be calculated as (assessment date – date of first dose of study drug + 1). For assessments conducted before the date of the first dose of study drug, study day is calculated as (assessment date – date of first dose of study drug). There is no study day 0.

In the situation where the event date is partial or missing, the date will appear partial or missing in the listings. Study day and any corresponding durations will be presented based on the imputations specified in Appendix 10.1.

Treatment duration: The treatment duration will be calculated as (date of the last non-zero dose of study drug - date of first dose of study drug + 1).

Baseline: the non-missing value most recently collected before the first dose.

All calculations and analyses will be conducted using SAS version 9.4 or higher.

# 6.2.2 Conventions

Unless otherwise specified, the following conventions will be applied to all analyses:

- 1 year = 365.25 days. Number of years is calculated as (days/365.25) rounded up to 1 significant digit.
- 1 month = 30.4375 days. Number of months is calculated as (days/30.4375) rounded up to 1 significant digit.
- Age will be calculated as the integer part of (date of informed consent date of birth + 1)/365.25
- P-values will be rounded to 4 decimal places. P-values that round to 0.0000 will be presented as '< 0.0001' and p-values that round to 1.000 will be presented as '> 0.9999'.
- Time-to-event or duration of event endpoints will be based on the actual date the radiograph was obtained rather than the associated visit date.
- Missing efficacy or safety data will not be imputed unless otherwise specified.
- For laboratory results collected as < or >, a numeric value, 0.0000000001 will be subtracted or added, respectively, to the value.
- For by-visit observed data analyses, percentages will be calculated based on the number of patients with non-missing data as the denominator, unless otherwise specified.

**Version 1.1**: 02/28/2020 Page 11 of 28

• For continuous endpoints, summary statistics will include n, mean, standard deviation, median, Q1, Q3 and range (minimum and maximum).

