# 6.5.2 Extent of Exposure

The number (and percentage) of patients requiring dose reductions, dose interruption, and treatment discontinuation will be summarized. One cycle is defined as 21 days of treatment except for the first cycle in the Phase 1 portion of this study.

The duration of treatment (months) will be summarized with descriptive statistics. It will be calculated as (Date of last non-zero dose – Date of first dose + 1) / 30.4375.

Number of patients with dose reductions and treatment discontinuation and their reasons, as well as number of patients with any dose modification will be summarized by counts and percentages according to study medication data. In addition, frequency of dose reductions and dose interruption will be summarized by categories  $(0, 1, \ge 2)$ .

Average dose intensity per patient (in mg/day) and relative dose intensity (total dose received / total dose planned) per patient will be summarized. Average dose intensity is calculated as the total dose (mg) taken by a patient divided by overall duration of exposure (= Date of last non-zero dose – Date of first dose + 1) for individual patient. Relative dose intensity is calculated as the total dose (mg) taken by a patient divided by the total dose planned for the patient by study design. To note, for the Phase 1 portion of the study, the planned dose for a patient will be a single dose on day 1 at a given dose level, no dose on day 2 and then twice daily for the next 21 days for Cycle 1; and then twice-daily for later treatment cycles. Patients in the Phase 2 portion of the study will always be treated on twice-daily administration at the prescribed dose level.

Patient data listings will be provided for all dosing records.

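### SAP 6.2.2 rounds months and years up to one significant digit, which taken literally turns 12.1 months into 20; it should be unrounded for analysis and one decimal place for display.

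*SAP*

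**What the plan says.** The list of conventions in SAP 6.2.2 opens with "Unless otherwise specified, the following conventions will be applied to all analyses". It then gives two conversions, "1 year = 365.25 days" and "1 month = 30.4375 days", each with its own rounding rule: "Number of years is calculated as (days/365.25) rounded up to 1 significant digit" and "Number of months is calculated as (days/30.4375) rounded up to 1 significant digit".

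The same list handles other quantities differently. For p-values it says "P-values will be rounded to 4 decimal places", and for age "Age will be calculated as the integer part of" a quotient, which is truncation.

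Months are named as a unit in four other places:

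- SAP 6.5.2: "The duration of treatment (months) will be summarized with descriptive statistics", followed by a formula that divides by 30.4375 and has no rounding step.
- SAP Appendix 10.2, part C3, which repeats that division for treatment duration, again without rounding.
- SAP 6.4.2, for the PFS time-point estimates (3 or 6 months), with OS handled in the same way.
- SAP 6.4.4, where the interval after the last platinum regimen is split at 12 months.

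The SAP states no unit for DOR, for time to response (TTR), or for median PFS and OS. Appendices 10.1 and 10.3 refer to a separate document of standard definitions and derivation rules, which is not among the documents reviewed.

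**The concern.** The sentence tells a programmer how the number of months is obtained, not just how it is printed. Rounded values could therefore enter the Kaplan-Meier analysis or a subgroup assignment as well as a table. One significant digit leaves a single usable figure: whole months below 10 and tens of months above. Rounding up makes the error one-sided.

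DOR is the key secondary endpoint. The background figures that a reader would set beside it, in Protocol 1.2, are medians of 9.2 and 7.9 months. Under the literal rule these would read 10 and 8. Because the p-value item in the same list speaks of decimal places, a programmer cannot simply assume that a significant digit means a decimal place.

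**Working it through.** **Inputs.** 365.25 days per year, 30.4375 days per month and the rounding rule come from SAP 6.2.2. The subgroup cut comes from SAP 6.4.4. The day ranges used for averaging are illustrations, not trial data.

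**1. The constants agree.** 365.25 / 12 = 30.4375 exactly. Only the rounding is at issue.

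**2. Literal rule.** For x months, let u = 10^k with k = floor(log10 x). The result is ceil(x/u) × u. For 12.1 months, u = 10, ceil(1.21) = 2, and the result is 20. In the same way 5.6 gives 6, 9.2 gives 10, 10.1 gives 20 and 20.1 gives 30.

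**3. Four readings side by side (months).**

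| Days | Exact | Up, 1 significant digit | Nearest, 1 significant digit | Up, 1 decimal | Nearest, 1 decimal |
|---|---|---|---|---|---|
| 91 | 2.990 | 3 | 3 | 3.0 | 3.0 |
| 183 | 6.012 | 7 | 6 | 6.1 | 6.0 |
| 335 | 11.006 | 20 | 10 | 11.1 | 11.0 |
| 369 | 12.123 | 20 | 10 | 12.2 | 12.1 |
| 487 | 16.000 | 20 | 20 | 16.0 | 16.0 |

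**4. Size of the error, averaged evenly over 1 to 730 days.**

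- Up, 1 significant digit: mean +3.61 months, maximum +9.99. No whole-day value is lowered or left unchanged; the first unchanged value is 2435 days, exactly 80 months.
- Nearest, 1 significant digit: mean -0.33 month, range -4.98 to +4.99. The one-sided bias goes, but the precision is still lost.
- Up, 1 decimal: mean +0.049 month, maximum +0.0998. In days, 0.05 × 30.4375 = 1.5 and 0.10 × 30.4375 = 3.0.
- Nearest, 1 decimal: mean +0.0003 month, largest error 0.05.

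On the year scale the literal rule behaves the same way. Up to 2000 days, only 1461 days (exactly 4 years) is unchanged.

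**5. Platinum-interval subgroup.** 305 / 30.4375 = 10.02 and 365 / 30.4375 = 11.99. If rounded months were used, all 61 whole-day values from 305 to 365 days would become 20 and move from the 6-12 month group to the group of 12 months or more.

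**6. Time-point estimates.** Between 1 and 10 months the literal rule rounds up to a whole month, so it does not carry an event across the 3- or 6-month mark. Those estimates could change only through new ties between events and censored times. Medians, quartiles and ranges are the exposed quantities.

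**7. Primary analysis.** With n = 80, a null rate of 30% and an assumed rate of 52%, the exact test rejects at 33 or more responders, with one-sided alpha 0.0211 and power 0.979, matching the stated 98%. The exact interval at 52% of 80 is 40.5% to 63.3%, as stated. No month or year value enters any of these.

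**The case against.** The strongest reply is that nobody would program the literal rule. A table in which 12.1 months appears as 20 would be noticed at once, and the rule sits badly with a subgroup cut at 12 months. One decimal place is the likely intent. On that reading the shift is at most about 3 days, well inside the ±7-day window for tumour assessments in Protocol 4.1.2.1, and if rounding up is loose wording for rounding there is no systematic bias. The convention also yields to more specific text: treatment duration has its own unrounded formula in SAP 6.5.2, and the separate derivation-rules document may settle the matter. All of this limits the likely effect. None of it corrects the sentence, and nothing in the supplied text overrides it for the other month-scale outputs.

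A reader might also infer more than the documents support:

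- *That every duration is biased upward.* Study day, and treatment duration as defined in SAP 6.2.1, stay in days. The clinical benefit threshold is in weeks. Age is truncated.
- *That all the errors flatter the drug.* Longer DOR, PFS and OS look favourable, but a longer TTR makes response look slower, and a longer treatment duration is an exposure measure with no plain direction.
- *That the platinum-sensitive cohort would change.* The literal rule does raise 153 to 182 days (5.03 to 5.98 months) to 6. However, platinum status is an eligibility definition in Protocol 4.2.1, and the SAP does not describe re-deriving it from rounded months.
- *That an inferential result is at risk.* Hypothesis testing is confined to ORR in platinum-sensitive patients. The time-to-event endpoints are descriptive.

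**Conclusion.** The rule is wrong as written and should be corrected, as a modest point. Applied literally, it makes month- and year-scale summaries unusable. That covers treatment duration, unless its own formula is read as overriding, and DOR, PFS, OS and TTR if they are reported in months, which is a reasonable inference but not stated. It could also misplace patients in the platinum-interval subgroup if rounded values feed that split. On the probable intent of one decimal place, rounding up leaves a small one-sided error of about 0.05 month on average and at most 0.10.

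Confidence is high about the text and the arithmetic. It is lower about the effect on results, because the derivation-rules document was not available and the programs may not follow the SAP sentence.

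**What to change.** Replace both sentences in SAP 6.2.2, for years and for months, with: *months = days/30.4375 and years = days/365.25, analysed unrounded and rounded to the nearest 1 decimal place for display only.* It follows that Kaplan-Meier input and the platinum-interval subgroup use unrounded values. Bring the separate derivation-rules document into line and check any programs already written against it.

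The cost is two sentences plus that check, with no change to design, data collection or sample size. SAP section 1 has the plan finalised before database lock, so the correction belongs before that point. If lock has passed, the study report should state which rounding was actually used.

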# 6.2.3 Handling of Missing Data

Missing data will not be imputed unless otherwise specified elsewhere in the SAP. Missing dates or partially missing dates will be imputed conservatively for adverse events and prior/concomitant medications/procedures. Specific rules for handling of missing or partially missing dates for adverse events and prior/concomitant medications/procedures are provided in Appendix 10.1.

By-visit endpoints will be analyzed using observed data, unless otherwise specified. For observed data analyses, missing data will not be imputed and only the observed records will be included.

At the time of primary analysis, if death or disease progression is not observed from a patient, corresponding censoring rules for OS, DOR and PFS will be followed.

#### 6.2.4 Adjustment for Covariates

No adjustments for covariates are planned for primary, secondary and exploratory analyses in the study.

# 6.2.5 Multiplicity Adjustment

No multiplicity adjustments will be made in this study. Two-sided 95% confidence interval (CI) will be used to describe the precision of the rate estimate whenever appropriate.

#### 6.3 SUBJECT CHARACTERISTICS

# 6.3.1 Subject Disposition

The number (percentage) of patients treated, discontinued from study treatment, entered survival follow-up visit (only for Phase 2), discontinued from study (including those who discontinued study treatment and did not enter survival follow-up, and those discontinued from the survival follow-up) and duration of follow-up will be summarized. The primary reason for study drug discontinued will be summarized according to the categories in the eCRF. The survival end of study status (alive, death, withdrew consent or lost to follow-up) at the data cutoff date will be listed using the data from the eCRF.

#### 6.3.2 Protocol Deviations

Major protocol deviation criteria will be established and patients with major protocol deviations will be identified and documented before the database lock.

Major protocol deviations will be summarized for all patients in the safety analysis set. They will also be listed by each category.

**Version 1.1**: 02/28/2020 Page 12 of 28

# 6.3.3 Demographic and Other Baseline Characteristics

Demographic and other baseline characteristics will be summarized in the safety analysis set, using descriptive statistics.

Continuous demographic and baseline variables include age, BMI, body weight, and height; categorical variables include age group (<65 years, ≥65 years), race, ECOG performance status and germline BRCA mutation type at study entry. In addition, disease characteristics include types of cancer, tumor staging, tumor diagnosis, target lesion diameter at study entry (for phase 2 only), CA-125 value at study entry (for phase 2 only) and time from initial diagnosis.

# 6.3.4 Prior Anticancer Drug Therapies and Surgeries

The number of prior anticancer drug therapies, prior anticancer radiotherapy and prior anticancer surgeries will be summarized in safety analysis set. The therapies with the same line number are counted as one prior therapy.

Previous anticancer medication will be summarized in the World Health Organization Drug Dictionary (WHO DD) preferred term, if data available.

#### 6.3.5 Prior and Concomitant Medications

Prior and concomitant medications will be coded using WHO DD and will be further classified to the appropriate Anatomical Therapeutic Chemical (ATC) code.

The number (percentage) of patients reporting prior and concomitant medications will be summarized by ATC medication class and WHO DD preferred term by phase in the safety analysis set. Prior medications are defined as medications that stopped before the first dose date. Concomitant medications will be defined as medications that (1) started before the first dose of study drug and were continuing at the time of the first dose of study drug, or (2) started on or after the date of the first dose of study drug up to 30 days after the patient's last dose or initiation of a new anticancer therapy. A listing of prior and concomitant medications will be provided.

#### 6.3.6 Medical History

Medical/disease history will be coded using the Medical Dictionary for Regulatory Activities (MedDRA, version 22.0 or higher). The number (percentage) of patients reporting a history of any medical condition, as recorded on the CRF, will be summarized by system organ class and preferred term in the safety analysis set. A listing of medical history will be provided.

#### 6.4 EFFICACY ANALYSIS

A summary table for all the efficacy endpoints could be referred to in Table 1. Detailed information for each endpoint for each phase is elaborated in the following subsections.

**Version 1.1**: 02/28/2020 Page 13 of 28

(Statistical Analysis Plan)

Table 1. Summary table of efficacy endpoints and their corresponding analysis sets

	Phase 1			Phase 2			Phase 2		
Phase (Source)	(Investigator Review)		(Independent Review Committee)			(Investigator Review)			
Analysis Set 	A	В	С	A	В	С	A	В	С
ORR	Y	Y	-	Y	Y	-	Y	Y	-
DOR	$Y^2$	-	-	$Y^2$	-	-	$Y^2$	-	-
PFS	-	Y	-	-	Y	-	-	Y	-
OS	-	-	-	-	-	-	-	Y	-
DCR	Y	Y	-	Y	Y	-	Y	Y	-
CBR	Y	Y	-	Y	Y	-	Y	Y	-
CA-125 response rate	-	Y 	Y 	-	-	-	-	$Y^3$	Y 

Note: 1: A: Efficacy evaluable analysis set, B: Safety analysis set, C: CA-125 evaluable analysis set, Y: Yes. 2: only for responders. 3: only for HGOC patients.

# 6.4.1 Primary Efficacy (Phase 2)

Hypothesis testing of ORR will only be performed in the patients with high grade platinum-sensitive ovarian cancer (PSOC). The primary analysis will be carried out using IRC data in efficacy evaluable analysis set. Efficacy endpoints based on investigator assessed tumor response will be presented as the sensitivity analysis. ORR of pamiparib per IRC is assumed as 52% in patients with recurrent PSOC. The historical rate in a similar population is estimated as 30%. The null and alternative hypotheses are set as follows:

H0: ORR=30% Ha: ORR >30%

A binomial exact test will be performed for hypothesis testing in recurrent PSOC efficacy evaluable analysis set. If the obtained one-sided p-value is  $\leq 0.025$ , it will be concluded that pamiparib monotherapy statistically significantly increases ORR compared with historical control. A two-sided binomial exact 95% CI of ORR will be constructed to assess the precision of the rate estimate.

The primary efficacy analysis will be conducted when mature response rate data have been observed, estimated as no more than 12 months after the last patient received the first dose of study drug.

Version 1.1: 02/28/2020 Page 14 of 28

ORR in evaluable recurrent high grade platinum-resistant ovarian cancer (PROC) will be summarized descriptively.

Sensitivity analysis of ORR will be carried out in the safety analysis set. Patients without postbaseline tumor assessment will be considered as non-responders in the safety analysis set and will be classified in category "not evaluated/not evaluable".

# 6.4.2 Secondary Efficacy (Phase 2)

Kaplan-Meier method will be used to estimate the key secondary endpoint, DOR, and corresponding quartiles (including the median) in the responders. A two-sided 95% CIs of median, if estimable, will be constructed with a generalized Brookmeyer and Crowley method.

Duration of response analysis will only include responders. Censoring rule for DOR will follow PFS censoring rule which will follow FDA Guidance for Industry Clinical Trial Endpoints for the Approval of Cancer Drugs and Biologics (2018).

Table 2 shows the primary censoring rules for the derivation of PFS using RECIST v1.1 criteria based upon investigator's tumor assessment.

Table 2. Censoring Rules for Analysis of Progression-Free Survival Per RECIST v1.1

No.	Situation	Date of Progression or Censoring	Outcome	
1	No baseline tumor assessments	Reference start date	Censored	
2	Progression documented on scheduled visit or between scheduled visits	Date of first radiologic PD assessment	Progressed	
3	No progression at the time of data cutoff or withdrawal from study	Date of last adequate radiologic assessment prior to or on date of data cutoff or withdrawal from study	Censored	
4	Treatment discontinuation for undocumented progression	Date of last radiological assessment of measured lesions	Censored	
5	New anticancer treatment started	Date of last radiological assessment of measured lesions prior to or on date of new anticancer treatment	Censored	
6	Death before first PD assessment	Date of death	Progressed	
7	Death between adequate assessment visits*	Date of death	Progressed	
8	Death or progression after two or more consecutive missed visit**	Date of last adequate radiologic assessment before missed tumor assessments	Censored	

Abbreviations: CR = complete response, PD = progressive disease, PR = partial response, SD = stable disease,

**Version 1.1**: 02/28/2020 Page 15 of 28

\* Adequate tumor assessment is a radiologic assessment of CR, PR, SD, non-CR/non-PD or PD as determined by investigators.

\*\*More than one missed visit is defined if the duration between the last tumor assessment and death or PD is longer than 2 scheduled visits.

Other time to event variables (PFS and OS) will be analyzed in the safety analysis set using the Kaplan-Meier method. The Kaplan-Meier estimates of PFS and OS will be plotted over time. The PFS time point estimates, defined as the percentages of patients in the analysis population who remain alive and progression-free at the specified time point (eg, 3 or 6 months), will be estimated using the Kaplan-Meier method along with the corresponding 95% CI constructed using Greenwood's formula. The OS time point estimates will be calculated similarly. For OS analysis, patient who has no death date in database will be censored at the last date the patient was known to be alive before/on cutoff date.

BOR is defined as the best response recorded from the start of pamiparib until data cutoff or start of new antineoplastic treatment. BOR and their 95% CIs will be summarized in the efficacy evaluable analysis set. Sensitivity analysis of BOR will be carried out in the safety analysis set. The proportion of each response category (CR, PR, SD, PD and NE) will be presented in the efficacy evaluable analysis set and safety analysis set.

DCR and CBR and their 95% CIs will be summarized in the efficacy evaluable analysis set and safety analysis set.

Time to response (TTR) is defined as time from first dose date to the date of earliest confirmed response (CR or PR) assessed using RECIST V1.1. Only responders were included in the analysis. TTR will be summarized descriptively.

All the efficacy endpoints in Phase 2 will be summarized by cohort. Assessments by IRC and investigator will be summarized separately.

The analysis of CA-125 response rate will be conducted on the CA-125 evaluable analysis set and safety analysis set. The analysis of change in CA-125 (the best percent change from baseline) will be conducted in the safety analysis set. Summary statistics, 2-sided 95% CIs, and graphical summaries will be generated for the percent change from baseline in CA-125. CA-125 definitions agreed by GCIG will be referred to calculate the CA-125 response rate.

#### 6.4.3 Efficacy Analysis (Phase 1)

For phase 1, there will be no analysis for OS. No IRC assessment is available for Phase 1 portion. For the rest part of the efficacy analysis, Phase 1 will follow what Phase 2 does, including the analysis of CA-125.

The efficacy analysis of Phase 1 will be presented by dose level and then separately, by cohort. The cohorts in Phase 1 will be:

- TNBC: triple negative breast cancer
- HGOC: high-grade epithelial, non-mucinous ovarian cancer, including fallopian cancer or primary peritoneal cancer

**Version 1.1**: 02/28/2020 Page 16 of 28

# 6.4.4 Subgroup Analyses (Phase 2)

Subgroup analyses of ORR will be conducted for PSOC patients in Phase 2. Table and forest plot of subgroup analysis in ORR will be provided based on the following subgroups:

- Age group (< 65 years vs.  $\ge 65$  years)
- Baseline ECOG performance status (0 vs. 1)
- Tumor stage at study entry (Stage I vs. II vs. III vs. IV vs. Unknown)
- BRCA mutation type (BRCA1 vs. BRCA2)
- Number of prior anticancer therapy lines (2 vs. 3 vs.  $\geq$ 4)
- Number of prior systemic chemotherapy lines (2 vs. 3 vs. ≥4)
- Name of the last surgery (Optimal debulking, Sub-optimal debulking, unknown, other)
- Time to progression to last platinum-based systemic chemotherapy (6-12 months vs. ≥ 12 months)
- Target lesion diameter at study entry (<50 mm,  $\ge50 \text{ mm}$ )
- CA-125 value at study entry (<70 kU/L),  $\ge 70 \text{ kU/L}$ )

These planned subgroup analyses may not be explored if sufficient number of samples cannot be achieved for certain subgroups. The subgroup variables and the cutoff values are subject to change if warranted to better represent the data.

